The use of an uroselective Alpha-1-antagonist to reduce the incidence and duration of postoperative urinary retention following spine surgery

NCT01568918

February 01, 2012

Title:

The Use of a Uroselective Alpha-1-Adrenergic Receptor Antagonist to Reduce the Incidence of Postoperative Urinary Retention Following Spine Surgery

Investigators:

[name]., [name]., [name], R.N., [name] (Statistician), [name] (Office of Research and Regulatory Support), [name], [name]., [name]. (Research Mentor), [name].

Abstract:

Postoperative urinary retention (POUR) occurs in up to 38% of neurosurgical patients undergoing simple decompressive spine procedures, with even higher rates estimated after complex spinal procedures such as instrumented fusion. This can result in multiple intermittent catheterizations for bladder decompression, increased incidences of urinary tract infection, and prolonged hospital stays. Previous non-neurosurgical series using nonspecific alpha-1adrenergic receptor antagonists have had some success in both the prevention and treatment of POUR. However, according to a recent Cochrane review, the use of alpha-blockers for the prevention and treatment of POUR is underresearched and there remains a need for well-designed clinical trials evaluating these drugs. The current neurosurgical practice at Mayo Clinic has both the clinical volume and infrastructure to support a randomized controlled trial evaluating the use of tamsulosin, a uroselective alpha-1-adrenergic receptor antagonist, for the prevention and treatment of POUR. If successful, this could not only result in decreased incidence and duration of POUR, but also in decreased hospital stays with an associated significant reduction in healthcare costs.

Background:

Postoperative urinary retention (POUR) is a common problem following neurosurgical procedures, specifically spine surgery. Estimates of incidence of POUR range from 2 to 69% in various surgical series depending on the type of surgery, anesthetic technique, and the method used to evaluate urinary retention.¹⁻⁸ In the only neurosurgical series specifically addressing the incidence of POUR, it was found to occur in 38% of patients undergoing simple decompressive spine surgeries with nearly an equal distribution between men

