Study subjects will be recruited through referral for surgical consultation in the neurosurgery outpatient clinic at Mayo Clinic Rochester. Individual surgeons will determine whether a surgery is indicated in particular patients. After the decision has been made to proceed with surgery, the patient will be interviewed for eligibility into the study, consented, and enrolled by the respective neurosurgeon's physician extender (R.N. or N.P.). Eligibility criteria are included in Table 1 and will be reviewed with each patient during the preoperative visit addressing the eligibility requirements for entry into the study. Patients undergoing simple spinal procedures (discectomy and foraminotomy procedures) that typically have next day hospital discharges and low incidences of POUR will be excluded from the study. It is not anticipated that subject retention will present a major challenge because the duration of study follow up is limited to the duration of the postoperative hospital stay. It is estimated that subjects will be actively participating in the study for approximately 8-12 days in most cases. Subject recruitment will continue until at least 175 subjects have been recruited into both the treatment and control groups and have completed the study. An interim analysis will be performed with unblinded data from the research pharmacy when 75 or more patients have completed participation.

Inclusion Criteria	Exclusion Criteria
≥ 35 years (Males & Females)	< 35 years
Cervical Laminectomy Cervical Posterior Fusion Cervical Anterior/Posterior Fusion	Cervical Anterior Discectomy and Fusion Cervical Anterior Corpectomy Cervical Posterior Discectomy Cervical Foraminotomy
Lumbar Laminectomy Lumbar Posterolateral Fusion Lumbar Interbody Fusion	Lumbar Discectomy (METRx or Open) Lumbar Foraminotomy Lumbar Anterior Fusion
	Myelopathy with bladder dysfunction
	Patients currently taking an alpha- antagonist [#]
	Patients with history of allergy or sensitivity to tamsulosin or other alpha-antagonist
	History of prostatectomy or urologic surgery involving the bladder or urethra
	Severe liver disease or end-stage renal disease

Table 1:

	Patients taking strong inhibitors of CYP3A4*
	Mental disability or prisoner

[#]The following drugs are alpha antagonists: alfuzosin, doxazosin, prazosin, terazosin, tamsulosin, and phenoxybenzamine.^{46,47}

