All statistical analysis and report of results will be done in a confidential manner and no information linking individual patients with data from the study will be shared outside of the study. Every effort will be made to keep this data anonymous once it has been collected.

Analysis of the Data:

Baseline characteristics will be compared between the two study groups using a chi-squared or Fisher's Exact Test for categorical variables and multiple two sample t-tests for continuous variables. The primary outcome variable, incidence of POUR, as well as other categorical variables, such as incidence of UTI, will be analyzed using a chi-squared test or Fisher's Exact Test. Duration of POUR will be compared using a two sample non-paired t-test comparing means. An appropriate nonparametric test (e.g. Wilcoxon Rank Sum) will be used for non-normal appearing data as can be anticipated for length of hospital stay. Differences in the groups with respect to baseline variables will be used to construct a multiple linear regression model to control for potential confounding factors if necessary. Intention to treat analysis will be used for all comparisons between groups.

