The primary outcome measure of incidence of POUR was used to calculate sample size. Data gathered from multiple series suggests that postoperative urinary retention occurs in 2-69% of patients undergoing a variety of surgical procedures, with 38% occurring in neurosurgical patients undergoing simple decompressive spinal procedures. Using 20% (P2=0.20) as a conservative estimate of incidence, an effect size of 10% for the primary outcome variable (P1=0.10) would be clinically meaningful. Thus, P2-P1 = 0.10. Because incidence of urinary retention is a binary categorical variable, a chi-squared test can be used to compare groups. Based on a type I error rate of 0.05 (α), a type II error rate of 0.20 (β), and power of 0.80 the estimated sample sizes needed for each group are as follows. For a one sided type 1 error, there would need to be 175 subjects in each group. For a two-sided type 1 error there would need to be 219 subjects in each group. A one-sided test of significance is reasonable in this study because an increase in incidence of POUR experienced in the tamsulosin treated group is not anticipated and would not add additional useful information in terms of using tamsulosin for POUR. Thus, a reasonable estimate for sample size is 175 subjects in both the treatment and control groups. Furthermore, with 175 patients per arm, there would be 87% power to detect a 1 day difference in the duration of urinary retention and duration of hospital stay with a 1-sided significance level of 0.05 (this assumes an effect size for this secondary outcome variable of 0.30 [1 day difference in means/pooled standard deviation estimate of 3.33]).

Role in Project:

[name]: Co-Principalinvestigator for the study, responsible for study design, study implementation, data collection, reporting of adverse events, and manuscript preparation.

[name]: Co-investigator responsible for assisting in study implementation, data collection, and manuscript preparation.

[name]: Co-investigator responsible for IRB application, Informed Consent form, and pharmacy liaison.

[name]: Statistician responsible for overseeing statistics performed by the co-PI as part of the CTSA BERD program.

[name]: Member of the Office of Research and Regulatory support who will be assisting with the Investigational New Drug application and corresponding with the FDA.

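### Does calling the 20% control rate conservative hide a shortfall in power at 175 patients per arm?

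*Combined protocol and SAP*

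**What the plan says.** The sample-size paragraph of Analysis of the Data first cites 2-69% retention across surgical series and 38% after simple decompressive spine surgery. It then sets the planning values: "Using 20% (P2=0.20) as a conservative estimate of incidence, an effect size of 10% for the primary outcome variable (P1=0.10) would be clinically meaningful", followed by "Thus, P2-P1 = 0.10". With a type I error rate of 0.05 and power of 0.80 it arrives at 175 per arm one-sided, which is adopted. For comparison it adds: "For a two-sided type 1 error there would need to be 219 subjects in each group". The same section says that the primary outcome "will be analyzed using a chi-squared test or Fisher's Exact Test".

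Other sections bear on the control rate. The Abstract says that retention "occurs in up to 38% of neurosurgical patients undergoing simple decompressive spine procedures". For larger operations it goes further: "with even higher rates estimated after complex spinal procedures such as instrumented fusion". The Background introduces the source of the 38% with the words "In the only neurosurgical series specifically addressing the incidence of POUR". Subject Recruitment and Retention says that patients having simple discectomy or foraminotomy, procedures "that typically have next day hospital discharges and low incidences of POUR will be excluded from the study".

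The plan gives power for the primary outcome at one pair of rates only. It states no relative risk, odds ratio or percentage reduction as a target.

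**The concern.** The only effect written as an equation is an absolute difference of 0.10. For a fixed absolute difference, the binomial variance grows as the rates approach 50%, so power falls. Choosing 20% when the document's own neurosurgical figure is 38% then raises the calculated power, which is the opposite of what *conservative* suggests to someone reading a sample-size justification.

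A higher control rate is also plausible. Fusion is eligible, the Abstract expects more retention after fusion, and low-incidence procedures are excluded. If the true rate were near 38% and the true benefit were 10 points, the trial would miss that benefit with probability of about 36% to 41%, against a planned 20%. A null result might then be over-read, and a reader might credit the design with a margin that it lacks. For 80% power on that reading, about 273 per arm (uncorrected) or 293 (corrected) would be needed.

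**Working it through.** **Inputs.** From Analysis of the Data: control rate 0.20, treated rate 0.10, alpha 0.05, power 0.80, equal arms, 175 per arm one-sided, 219 two-sided. From the same section and the Abstract: 0.38 as the alternative control rate. Normal quantiles: 1.645 (one-sided 0.05), 1.960 (two-sided 0.05), 0.842 (power 0.80).

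**Step 1: reproduce the plan's figure.** Write pc and pt for the control and treated rates, d = pc − pt, and p = (pc + pt)/2.

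`n = [z_alpha*sqrt(2p(1−p)) + z_beta*sqrt(pc(1−pc) + pt(1−pt))]^2 / d^2`

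Here 2p(1−p) = 2 × 0.15 × 0.85 = 0.255, and the sum of variances is 0.16 + 0.09 = 0.25.

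- One-sided: (1.645 × 0.505 + 0.842 × 0.5)² / 0.01 = 156.6.
- Two-sided: (1.960 × 0.505 + 0.842 × 0.5)² / 0.01 = 199.0.

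Continuity correction: `n_cc = (n/4)*[1 + sqrt(1 + 4/(n*d))]^2`, which gives 176.0 one-sided and 218.5 two-sided. The plan has 175 and 219. It names no correction; I infer one because the uncorrected values (157 and 199) are far off. The one-subject gap on the one-sided figure is immaterial: exact enumeration of a one-sided Fisher test at 175 per arm gives 80.5% power.

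**Step 2: power at 175 per arm, one-sided 0.05.**

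`power = Phi{ [d − c − 1.645*sqrt(2p(1−p)/175)] / sqrt((pc(1−pc) + pt(1−pt))/175) }`

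with c = 1/175 = 0.0057 for the corrected version and c = 0 otherwise.

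- 20% vs 10%: (0.1 − 0.0628)/0.0378 = 0.985, power 0.838; corrected (0.1 − 0.0057 − 0.0628)/0.0378 = 0.833, power 0.798.
- 38% vs 28%: (0.1 − 0.0827)/0.0500 = 0.346, power 0.6355; corrected (0.1 − 0.0057 − 0.0827)/0.0500 = 0.232, power 0.592.

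Exact enumeration agrees: at 38% vs 28%, about 59% for Fisher and 64% for the uncorrected test.

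**Step 3: carry the plan's effect to 38% on each scale.** The pair 20% and 10% fits three descriptions: a 10-point drop, a halving, and an odds ratio of (0.10/0.90)/(0.20/0.80) = 0.444. At 38% these part company. The odds are 0.38/0.62 = 0.613; multiplied by 0.444 they become 0.272, a treated rate of 0.272/1.272 = 21.4%.

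| Control vs treated | What is held constant | Reduction (points) | Power, corrected | Power, uncorrected |
|---|---|---|---|---|
| 20% vs 10% | the plan's own pair | 10 | 80% | 84% |
| 38% vs 28% | absolute difference | 10 | 59% | 64% |
| 38% vs 21.4% | odds ratio 0.444 | 16.6 | 95% | 96% |
| 38% vs 19% | halving | 19 | 99% | 99% |

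Below 20% the order reverses. At an illustrative control rate of 15% (my assumption, not the plan's), power is 91%/93% for 10 points and 66%/72% for a halving.

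**Step 4: where the boundary lies.** For 10 points, 80% power holds up to a control rate of 19.9% (corrected) or 22.2% (uncorrected). At 38%, 80% power needs a reduction of 12.9 or 12.3 points. Relative to 38% that is 12.9/38 = 34% or 12.3/38 = 32%, less than the 50% reduction in the plan's own pair.

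**The case for a change.** The strongest case for a change is that an absolute difference is the only scale the plan puts in an equation. A reader cannot tell whether power at 38% is about 60% or 99%. The 38% is the plan's own figure, most of its remarks on incidence point upward, and no reason is given for moving down to 20%. Removing one adjective and adding a line of power figures would cost almost nothing.

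Much of this stands. The arithmetic is right, and the plan does leave open the scale on which the effect is expected to hold.

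Three things do not carry over:

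- The adjective qualifies the estimate of incidence, directly after higher published figures. Its plain sense is a low, cautious guess at how often retention occurs. No margin in power is claimed.
- The 10 points are introduced with 20% as the stated base, and the equation is the subtraction of the two rates. Nothing says that 10 points is the target at every control rate. Going from 38% to 28% is a 10/38 = 26% relative reduction, about half the relative effect in the plan's pair.
- The 38% is not an established rate for this population. The Abstract words it as an upper figure, it comes from one series, and Table 1 excludes myelopathy with bladder dysfunction and prior urologic surgery, which may lower the rate.

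**Conclusion.** The concern does not call for a change. The plan states one power claim for the primary outcome, 80% for 20% against 10%, and 175 per arm meets it (80% corrected, 84% uncorrected). The figure of 59% to 64% is correct only under two assumptions that the plan does not join: a control rate of 38% and a benefit that stays at 10 points. If the benefit scales with the baseline risk, the same 350 patients give 95% to 99% power at 38%. Whether 20% is cautious for power therefore depends on an effect scale that the plan leaves open, and the word cannot be shown to be wrong.

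Settling the scale would also gain nothing for the trial. The number of patients, the chi-squared or Fisher test, the conduct and the result are the same either way, because neither test uses the planning effect. Any risk of over-reading a null result is met when the results are read, through the confidence interval for the difference. Its expected 95% half-width is `1.96*sqrt((pc(1−pc) + pt(1−pt))/175)`: 1.96 × sqrt(0.25/175) = 7.4 points at 20% vs 10%, and 1.96 × sqrt(0.4372/175) = 9.8 points at 38% vs 28%. Either width shows directly whether a 10-point benefit has been excluded. What remains is a missing line of explanation.

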Hypothesis 2: Tamsulosin started five days preoperatively and taken until hospital discharge will significantly decrease the **duration** of postoperative urinary retention among neurosurgical patients undergoing decompressive laminectomy and/or spinal fusion procedures who experience this surgical complication compared to placebo. (Secondary Hypothesis) Hypothesis 3: Tamsulosin started five days preoperatively and taken until hospital discharge will significantly decrease the length of hospital stay among neurosurgical patients undergoing decompressive laminectomy and/or spinal fusion procedures compared to placebo. (Secondary Hypothesis)

Specific Aims:

- 1) To determine if the use of a uroselective alpha-1-adrenergic receptor antagonist during the perioperative period reduces the incidence and duration of POUR in neurosurgical patients undergoing decompressive laminectomy and/or spinal fusion.
- 2) To determine if reduced incidence and duration of POUR in this patient population will result in decreased length of hospital stay.

Experimental Design:

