Secondary outcome variables include duration of POUR among those patients in which it occurs, number of intermittent catheterizations in those with urinary retention, incidence of UTI, and duration of hospital stay. Measurement of the duration of POUR will closely coincide with the methods for recording incidence of POUR as discussed above. The decision to use and the time of removal of indwelling urinary catheters will be left to the discretion of the primary neurosurgical team. Time of indwelling catheter removal after surgery will serve as time zero for beginning calculation of postoperative urinary retention duration if the patient later requires in and out straight catheterization. For patients without an indwelling catheter, the time patients leave the operating room will serve as time zero. Per the Urinary Retention Protocol (MC1156-214rev0610),

patients found to be experiencing POUR will be ordered to have a straight in and out catheterization performed by a member of the catheterization team after failure of noninvasive measures (e.g. trigger techniques, bladder massage, application of warmth, relaxed environment, privacy, ambulation) by the attending nursing staff member. Urinary retention will be considered resolved after two consecutive post-void residual urine scans have demonstrated less than 300 ml residual urine volume in a patient spontaneously voiding. The number of intermittent catheterizations is recorded in the EMR in accordance with the standardized protocol.

Patients suspicious of having a UTI based on signs and symptoms of urinary frequency, urgency, burning or pain will have a urine sample (via catheterization or spontaneous void) sent for routine urinalysis, gram stain, and culture/sensitivity by the nursing staff member responsible for the patient or the primary neurosurgical team, per instructions documented on the Urinary Retention Protocol (MC1156-214rev0610). Positive UTIs will be defined as positive gram stain in the presence of signs or symptoms of UTI, urine white blood cell count elevation, and positive culture of >10⁴ cfu/ml. Patients will be treated with the appropriate antibiotic based on culture sensitivity.

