Length of hospital stay will be recorded for all patients following the surgical procedure with the day after surgery defined as postoperative day one. The medical record will be reviewed following discharge to determine if hospital discharge date was dependent on POUR or other reason (e.g. uncontrollable pain, mobility requiring physical therapy or inpatient rehabilitation, or other medical complications delaying discharge).

In addition to the primary and secondary outcome measures, baseline characteristics will be collected on all patients via the medical record including age, height and weight, past history of postoperative urinary retention or diagnosis of benign prostatic hyperplasia (not on treatment), length and type of surgery, estimated blood loss during surgery, total intravenous fluids administered perioperatively, time to oral analgesic use (in hours), total analgesic use during the postoperative period, time to first postoperative mobility (in hours), and any adverse events thought to be related to administration of the study medication. These variables will be used as baseline comparisons between the two groups to ensure homogeny and be used in statistical adjustment if differences between the groups are significant after randomization.

Unanticipated events:

There is the potential for patients to experience urinary retention as outpatients after inpatient urinary retention has resolved. This is quite unusual to occur after urinary retention has resolved as defined above and may indicate the patient needs further investigation by a urologic surgeon. Patients will be counseled by nursing staff prior to dismissal regarding the signs and symptoms of urinary retention and directed to seek medical attention with appropriate urology referral should the treating physician deem this is appropriate.

Patients experiencing prolonged postoperative urinary retention (> 5 days) will be seen by the urology consult service for recommendations regarding further investigation and treatment. The study group designation may be broken at this point to determine which group the patient is in regarding treatment medication if deemed necessary by the urology consult service to guide further treatment.

Patients experiencing severe adverse events such as profound hypotension, arrhythmia, or allergic reaction will be evaluated by the primary neurosurgical team with appropriate intervention or consultation as deemed necessary.

Quality Control:

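### The 87% power for a 1-day difference in duration of POUR counts all 175 patients per arm, but only POUR cases enter that comparison; on the plan's own rates and SD it is about 26%

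*Combined protocol and SAP*

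**What the plan says.** Analysis of the Data sizes the trial on incidence of POUR: "Using 20% (P2=0.20) as a conservative estimate of incidence, an effect size of 10% for the primary outcome variable (P1=0.10"). That gives 175 patients per group with a one-sided test. The same paragraph then adds that "with 175 patients per arm, there would be 87% power to detect a 1 day difference in the duration of urinary retention" and extends the claim to "duration of hospital stay with a 1-sided significance level of 0.05". The inputs are given in brackets: "this assumes an effect size for this secondary outcome variable of 0.30 [1 day difference in means/pooled standard deviation estimate of 3.33".

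Two other places fix who contributes to the duration comparison. Outcome Measures lists "duration of POUR among those patients in which it occurs" as the secondary outcome. Hypothesis 2, under Rationale, limits the claim to patients "who experience this surgical complication compared to placebo". The planned test is also stated in Analysis of the Data: "Duration of POUR will be compared using a two sample non-paired t-test comparing means".

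**The concern.** Power depends on the number of patients who supply a value to the test. Hospital stay is recorded for every patient, so 175 per arm is the right count there. Duration of POUR exists only for patients who have POUR, and at the planning rates that is a small minority of each arm. One power figure has been applied to two outcomes with very different denominators.

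Duration is the subject of a named secondary hypothesis and part of Specific Aim 1. A reader who trusts 87% would take a non-significant result as fairly strong evidence against a 1-day benefit, since such a benefit should be missed only about one time in eight. If the true power is far lower, a null result says little.

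**Working it through.** **Inputs, all from the plan.** 175 per arm; one-sided alpha 0.05; difference 1 day; SD 3.33, so d = 1/3.33 = 0.30; POUR rates 20% (placebo) and 10% (tamsulosin); two-sample t-test.

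**Formula.** With n1 and n2 patients contributing, the noncentrality is d / √(1/n1 + 1/n2) on n1 + n2 − 2 degrees of freedom. Power is the probability that the noncentral t exceeds the one-sided 5% critical value.

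**Step 1: reproduce the plan's figure.** n1 = n2 = 175: noncentrality 0.30 / √(2/175) = 2.81, power 87.6%. This matches the stated 87%, so the formula is sound and all 175 patients per arm were counted.

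**Step 2: count the patients who have a duration.** Placebo 175 × 0.20 = 35; tamsulosin 175 × 0.10 = 17.5.

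**Step 3: recompute.** Noncentrality 0.30 / √(1/17.5 + 1/35) = 1.02, power 26.3%. Whole numbers of tamsulosin cases give 26.0% (17) and 26.6% (18). Averaging over binomial case counts gives 26.0%.

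**Step 4: detectable difference.** With 17.5 and 35 cases, 80% power needs d = 0.738, which is 0.738 × 3.33 = 2.46 days.

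**Step 5: vary the incidence, keeping SD 3.33.** The plan cites 38% for simple decompressive spine surgery and 69% as the top of the range across surgical series. The tamsulosin rates below are scenarios.

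| Placebo / tamsulosin rate | Cases (placebo / tamsulosin) | Power for 1 day |
|---|---|---|
| 20% / 10% | 35 / 17.5 | 26% |
| 38% / 19% | 66.5 / 33.25 | 40% |
| 38% / 28% | 66.5 / 49 | 48% |
| 38% / 38% | 66.5 / 66.5 | 53% |
| 69% / 34.5% | 120.75 / 60.4 | 60% |
| 69% / 69% | 120.75 / 120.75 | 75% |

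Reaching 87% at d = 0.30 takes about 172 POUR cases per arm, so nearly every patient would have to develop retention.

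**Step 6: vary the SD.** The plan gives no SD specific to POUR cases, so these values are assumptions. At 17.5 and 35 cases, SDs of 2.5, 2.0 and 1.5 days give 38%, 52% and 73%. The SD that would yield 87% for 1 day is about 1.2 days at 20%/10%, 1.7 at 38%/19% and 2.1 at 38%/38%.

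**Step 7: would zeros for patients without POUR rescue it?** Let mc and mt be the mean durations among placebo and tamsulosin cases. At 20%/10%, a 1-day difference over all patients needs 0.20·mc − 0.10·mt = 1. If tamsulosin cases last no time (mt = 0), mc = 5 days. If they are 1 day shorter (mt = mc − 1), then 0.10·mc + 0.10 = 1 and mc = 9 days. Under Unanticipated events the plan treats durations beyond 5 days as exceptional: "Patients experiencing prolonged postoperative urinary retention (> 5 days") are referred to urology.

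**The case against.** The strongest objection is to the 26%, not to the mismatch. The plan gives one SD in a sentence that covers both retention and hospital stay, and it may really be a hospital-stay figure. If retention seldom lasts beyond 5 days, an SD of 3.33 among cases may be too large and 26% too low. That stands as a caution: 26% follows from the plan's only SD, and Step 6 shows how power rises with smaller values. It does not support 87%, which at 20%/10% needs an SD near 1.2 days, a value the plan neither states nor uses.

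A second objection is that 20% was chosen as a conservative rate and that the authors expected more POUR, especially after fusion. This narrows the gap but does not close it at SD 3.33, as Step 5 shows.

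A third is that an intention-to-treat comparison could count patients without POUR as zero days. The numerical check in Step 7 is specific to 20%/10%. At 38%/19% the same equation needs mc = 1/0.38 = 2.6 days if mt = 0, or mc = 0.81/0.19 = 4.3 days if tamsulosin cases are 1 day shorter, and neither is implausible on the plan's 5-day marker. Beyond the planning rates the answer therefore rests on the text: the plan nowhere assigns a zero, and both Hypothesis 2 and Outcome Measures confine duration to patients with POUR.

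Finally, the outcome is secondary and did not drive enrolment. That is true and limits the consequence, but the stated figure is still wrong for the outcome it names.

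**Conclusion.** The concern holds. The 87% is correct for a comparison of all 175 patients per arm and does not apply to duration of POUR as the plan defines it. On the plan's rates and SD, a true 1-day difference would be missed about three times in four, not about one time in eight. The size of the shortfall depends on the SD among POUR cases, which the plan does not give, and on the incidence. That 87% is unsupported for this outcome rests on less: only that patients without POUR do not enter the comparison and that the SD is the one stated. The primary sample size, and the 87% for a mean difference in hospital stay, are unaffected.

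**What to change.** In the sample-size paragraph of Analysis of the Data:

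- Withdraw the 87% for duration of POUR.
- State that about 35 placebo and 17 to 18 tamsulosin patients are expected in that comparison at 20%/10%.
- State that power for a 1-day difference is about 26% at SD 3.33, that 80% power is reached at about 2.5 days, and give the range for higher incidence or smaller SD. If a smaller SD among POUR cases is preferred, give it with its source.
- Keep the 87% for hospital stay, labelled as t-test power for a 1-day mean difference over all randomised patients, since the plan anticipates a rank-based test for that outcome.

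The cost is wording only. One stated figure becomes less favourable; there are no extra patients and no change to the primary sample size, tests or endpoints.
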